Patients will be selected and included during consultations with the investigating dental surgeons. Once a diagnosis requiring first-level endodontic treatment or re-treatment is given, the investigator will offer the patient the opportunity to participate in the study and will seek to obtain their consent after introducing them to the study, in accordance with Good Clinical Practice.

Once the endodontic treatment has been completed and the permanent coronal restoration has been carried out, patients will be monitored regularly for 2 years, with 3 follow-up visits scheduled: at 6 months, 12 months and 24 months. At each visit, a clinical examination and a retro-alveolar X-ray will be carried out to assess the results of the treatment.

At the end of the 24-month follow-up period, only patients treated with the PA1704 ready-to-use filling material will be offered the option of continuing

the clinical follow-up for up to 5 years; in which, at their annual dental check-up in the 4th and 5th years following the endodontic treatment, a clinical examination and a retro-alveolar X-ray will be performed to assess the results of the treatment.

Study procedure:

V0 — Selection visit:

- diagnosis (preoperative 2D retro-alveolar X-ray) and verification of eligibility,
- oral information about the trial and delivery of patient information and consent form,

V1 — Enrolment visit

- Collection of written consent
- Recording in the eCRF of **patient characteristics at enrolment** (sex, age, oral-dental status, history and treatments) AND characteristics of the **tooth to be treated** [tooth number, number of canals to be filled, initial or repeat endodontic treatment, pulpal and periapical diagnosis, preoperative pain (if root canal preparation and filling are carried out over several sessions, preoperative pain is recorded at the start of each session)].
- Randomization (PA1704 vs BioRoot™ RCS filling material).
- Endodontic treatment in 1 or 2 sessions depending on each practitioner's usual practice and the clinical situation (initial or repeat endodontic treatment): 1) removal of the old filling material in case of retreatment, 2) root canal preparation, 3) standardized root canal obturation (obturation cements will be used with Gutta-Percha cones in accordance with the manufacturer's recommendations using the single cone technique or cold lateral condensation),
- Immediate post-operative **X-ray check** (=T0) to verify the level of the apical filling.

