6.1. General points and methodology

✓ Methodology — trial design

Prospective, multicenter, randomized, controlled, open-label study, with blind evaluation of the primary criterion and several secondary criteria (PROBE design).

Parallel group design (1:1):

- The arm receiving the device under investigation: PA1704
- The arm receiving the comparator medical device: BioRoot™ RCS.

✓ Measures to reduce or avoid bias.

Randomization and stratification:

Before the trial is set up, the CRO's biostatistician will computer-generate a block randomization list stratified by clinical indication (initial endodontic treatment (ET) versus re-treatment (ER)). The randomization system will be integrated directly into the electronic CRF.

Randomization will be carried out by the electronic CRF once the eligibility criteria have been checked, the clinical indication (ET or ER) has been determined and all this information has been recorded in the specific module by the investigator.

It should be noted that the proportion of ERs will be 30% of the overall sample, which is close to the rate reported in a French Health Insurance survey (Masson 2002). The rate of ER may vary between sites: some investigators, because of their specialty in endodontics, will include a majority of patients with an indication for re-treatment, whereas GP investigators will probably have more indications for first-line treatment.

Blind:

Investigators and patients will not be blind to the medical device allocated due to the different ways in which the 2 products are presented and used. On the other hand, two independent qualified assessors (previously calibrated under the supervision of the study coordinator) will conduct the blind, centralized review of the retro-alveolar X-rays taken at TO (reference radiograph obtained immediately post-operatively), 6 months, 12 months, 24 months, 3.5 years and 5 years (Refer to Section "Equipment to be used to evaluate clinical trial variables and arrangements for monitoring maintenance and calibration." section of this chapter); they will be blinded to centre, patient, indication (initial or repeat endodontic treatment), and treatment arm; the files will first be anonymized by the CRO.

✓ Outcome measures

Primary criterion (composite criterion):

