6.3. Selection of subjects for the study

✓ Study population

Patients requiring first-line or repeat endodontic treatment and meeting the eligibility criteria described in the following paragraph will be able to take part in the trial.

Patients taking part in this clinical trial will not be able to take part in any other trial. However, there is no exclusion period at the end of this trial for participation in any other study.

✓ Inclusion criteria for patient selection.

The characteristics required for a patient to be included in the trial are:

- Men or women aged over 18 years,
- Patients requiring endodontic treatment on a single tooth, in accordance with the latest HAS
 recommendations; treatment may be first-line (ET) or repeat (ER), on a monoradiculated or
 pluriradiculated tooth.
- A patient who is geographically stable and/or regularly monitored by the practice, and who can be monitored for 2 years,
- Patients who have signed their consent form,
- Patients affiliated to a social security / insurance scheme (Art L1121-11 of CSP).

✓ Non-inclusion criteria for subject selection.

The following characteristics exclude certain subjects from inclusion in the trial:

Dental exclusion criteria:

- Patients with a formal contraindication to endodontic treatment,
- Patient with a known contraindication to the use of BioRoot™ RCS or PA1704 filling material: endodontic treatment on immature or provisional teeth, known hypersensitivity to any of the compounds in the formula.

Exclusion criteria related to participation in the clinical trial:

Patients meeting at least one of the following criteria cannot be included in the study.

These criteria are not contraindications to the use of a permanent root canal filling material, but the first 4 on the list are confounding factors known to negatively influence healing rates and prognosis:

- Endodontic treatment of a tooth with a calcified root canal,
- Endodontic treatment of teeth with suspected perforation,
- Patients with a non-stabilized systemic disease such as diabetes or thyroid disorders, or who are immunocompromized or have undergone radiotherapy of the jaw.
- Patients suffering from active non-stabilized and untreated periodontitis.
- Simultaneous participation in another interventional trial,

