- **Randomization** of the medical device (PA1704 or BioRoot™ RCS) stratified according to endodontic treatment indication (randomization system integrated in the eCRF).
- **Endodontic treatment** over 1 or 2 sessions, depending on the usual practice of each practitioner and the clinical situation (initial or repeat endodontic treatment) and following the instructions for use of the PA1704 or BioRoot™ RCS filling materials (see instructions above).

Record of data describing operating procedures in the eCRF: 1) preparation of the canal (technique for removing the old material in the event of re-treatment), 2) shaping and cleaning of the canal (instruments used, irrigation solutions and techniques, rinsing solution, drying), 3) number of gutta-percha cones used and condensation technique.

- Immediate post-operative X-ray check (=T0; reference image for patient follow-up; reminder: the entire tooth from the *crown to the apex, including the root* must be visible in the image):
 - Evaluation of the level of obturation at the X-ray apex for each canal,
 - Evaluation of obturation density (radiopacity and presence of voids),
 - Upload the T0 image to the eCRF.
- **Quality coronal restoration**: the reconstruction can be either temporary or permanent if the conditions are right and according to the practitioner's habits. In all cases, the restoration must be watertight and made using glass ionomer cement or a composite (see recommendations above). Exclusive endodontic investigators must ensure watertight reconstitution.
- Explanations and handing over of the **patient record** for recording pre-operative and post-operative pain over 7 days, painkillers and AEs. The preoperative and T0 VAS is completed in the office in the presence of the dental surgeon or dental assistant in order to check that the evaluation tool has been properly understood; it should be noted that if the root canal preparation and filling are carried out over 2 sessions, preoperative pain levels will be recorded at the beginning of each session).
- Scheduling the **next consultation**: either the V2 visit to perform the standard permanent coronal restoration (if the restoration was temporary at V1 i.e. within 45 days), or the V3 follow-up visit at 6 months if the permanent coronal restoration was performed at V1.

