No interim analysis of the primary criterion is planned. The main analysis will only be carried out after the 2-year follow-up of all patients enrolled.

Two interim analyses of the secondary criteria have been planned. These will be carried out after 6 and 12 months' follow-up for all included patients.

The alpha risk will not be inflated, as the main criterion will not be analyzed in the interim analyses. Therefore, no alpha risk adjustment method is required. The final analysis will focus on the primary and secondary criteria.

For patients treated with the PA1704 ready-to-use filling material and who agree to be followed-up with for up to 5 years, a non-comparative descriptive analysis of secondary performance and safety criteria at 3.5 years and 5 years will be carried out at the end of their participation.

7.7.8. Criteria for stopping the clinical trial from a statistical point of view:

None. Interim analyses are only used to collect data on secondary criteria before the end of the study. The conclusion on the non-inferiority of PA1704 compared to BioRoot™ RCS will only be made on the final analysis at 2 years.

7.7.9. Changes to the statistical analysis plan:

The statistical analysis plan will be drawn up before the first interim analysis is carried out. The initial analysis strategy may undergo minor modifications following each data review, and the new statistical analysis plan will be described in detail at that time.

7.7.10. Specification of sub-groups for further analysis:

The following sub-group analyses will be carried out, at least on the PP population, during the final analysis at 2 years. Other factors not considered in this protocol may be added in the Statistical Analysis Plan.

- For the primary criterion, the rate of effective treatment at 2 years:
 - Prognostic factors at enrolment
 - Presence or absence of a periapical lesion,
 - Indication for endodontic treatment: initial versus repeat endodontic treatment,
 - Factors related to the surgical procedure
 - Type of rinse solution used to finalize root canal disinfection,
 - Operating techniques used: technical platform used (whether or not a microscope was used), manual files versus continuous rotation versus alternative rotation.
- Post-operative pain:
 - Operating techniques used: manual files versus continuous rotation versus alternative rotation.
 - Initial pulp pathology (pre-existing inflammatory situation or necrosis or live pulp),

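### Allocation is released before canal preparation although the arms share the same steps until the sealer is prepared, and a randomised tooth that is never filled enters no analysis set

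*Combined protocol and SAP*

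**What the plan says.** **Trigger for randomisation.** Section 6.1: "Randomization will be carried out by the electronic CRF once the eligibility criteria have been checked" and the indication (initial or repeat treatment) has been recorded. Completion of canal preparation is not a condition.

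**Order at V1.** Section 6.5.2 puts the randomisation step, "stratified according to endodontic treatment indication (randomization system integrated in the eCRF"), ahead of the treatment step. The synopsis (2.1) has the same order and lists what follows: "1) removal of the old filling material in case of retreatment, 2) root canal preparation, 3) standardized root canal obturation".

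**Sessions.** Treatment is given "over 1 or 2 sessions, depending on the usual practice of each practitioner and the clinical situation". Preparation and filling may be separated: "if the root canal preparation and filling are carried out over 2 sessions, preoperative pain levels will be recorded at the beginning of each session".

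**Blinding.** Section 6.1: "Investigators and patients will not be blind to the medical device allocated". The two X-ray assessors are blind to arm through 24 months.

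**Steps by arm.** In Table 5 (6.5.1) the first three canal steps (clean and shape, fit the master cone, rinse and partly dry) are the same for both devices. The columns diverge when the syringe is opened or the powder and liquid are mixed.

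**Analysis sets (7.6).** Tolerance covers patients treated with either device. The mITT set requires treatment with a device and at least one efficacy assessment. PP, the primary set (7.7.4), is a subset of mITT that also needs the primary criterion. Withdrawn patients are not replaced (6.3). Nothing is imputed, except that failure at 6 or 12 months counts as failure at 24 months (7.7.11).

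**The concern.** The allocated material is first needed at obturation, but the allocation is available before removal of old material, shaping and disinfection, and in two-session cases possibly a session earlier. Section 3.1.2 itself says that technical factors affect efficacy. Open label is unavoidable while the sealer is handled. It is avoidable during the steps before that.

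Three things are at stake:

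- **Performance bias.** Preparation could drift with knowledge of the arm. Blind X-ray reading protects the assessment, not the preparation.
- **Loss after randomisation.** If treatment stops between allocation and filling, for any reason, the patient has an assigned arm but belongs to no analysis set. The plan does not say how a tooth found unsuitable during preparation is to be handled in the analysis.
- **Subgroups.** Section 7.7.10 plans subgroups under "Factors related to the surgical procedure", including the final rinse and the file type. Under the present order these are chosen after allocation, so randomisation does not protect those comparisons.

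**Working it through.** **1. When the arm becomes known.** No single sentence says that operators know the arm during preparation. It follows from three facts together: the eCRF allocates after the eligibility and indication entries (6.1); preparation comes after allocation (2.1, 6.5.2); and the label is open with no step that withholds the result.

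**2. What happens to a randomised, unfilled tooth.** It is not treated with a device, so it is not in Tolerance and not in mITT. PP is a subset of mITT, so it is not in PP either.

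**3. The plan's sample size.** Inputs (7.2, 7.3): 90% in both arms, margin 13 points, one-sided alpha 5%, power 80%.

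n = 2 × 0.9 × 0.1 × (1.645 + 0.842)² / 0.13² = 65.85, so 66 per arm, as stated. Then 66 × 1.20 = 79.2, so 80, also as stated. The timing of allocation does not alter the 66.

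**4. Effect of loss before filling on power.** The documents give no rate, so 2%, 5% and 10% are assumptions, combined with 20% later drop-out.

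Evaluable per arm m = 80 × (1 − loss) × 0.80. Power = Φ(0.13 / √(0.18/m) − 1.645). Randomised per arm needed to keep 66 evaluable = 66 / (0.80 × (1 − loss)), rounded up.

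| Assumed loss before filling | Evaluable per arm | Power | Randomised per arm to keep 66 |
|---|---|---|---|
| 0% | 64.0 | 79% | 83 |
| 2% | 62.7 | 78% | 85 |
| 5% | 60.8 | 77% | 87 |
| 10% | 57.6 | 75% | 92 |

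The first row shows that part of the shortfall comes from the 20% inflation method and has nothing to do with this point.

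**5. Effect of selective loss on type I error (constructed case).** Take true rates at the margin: 0.90 for the comparator and 0.77 for PA1704, with 66 per arm. Suppose k PA1704 teeth that would have failed leave before filling and none leave the comparator arm.

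p′ = 0.77 × 66 / (66 − k); SE = √(0.9 × 0.1/66 + p′(1 − p′)/(66 − k)); type I error = 1 − Φ(1.645 − (p′ − 0.77)/SE).

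| k | p′ | One-sided type I error |
|---|---|---|
| 0 | 0.770 | 5.0% |
| 1 | 0.782 | 7.3% |
| 2 | 0.794 | 10.4% |
| 3 | 0.807 | 14.6% |

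If the selective loss fell in the comparator arm instead, the error would move the other way. The table shows how few patients it takes. It does not show what is likely.

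**The case against.** The plan contains no contradiction here, and several safeguards exist.

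- **Technique is constrained.** Sodium hypochlorite is mandatory and practitioners keep to their usual practice (6.2), which ties technique to the operator more than to the arm. Both sealers are tricalcium silicate cements used with gutta-percha by the same cold techniques, and the documents suggest no reason why knowing the sealer would change shaping. This lowers the likelihood of drift but does not exclude it.
- **Drift and losses are partly visible.** Operative technique is recorded (6.5.2) and compared between arms (7.7.5). Early departures are tabulated with reasons (7.7.1). X-rays are read blind. These can reveal a difference in preparation. They cannot prevent it, and they do not return an unfilled patient to an analysis.
- **The 20% allowance** may already cover some loss before filling. The power figures above add the assumed loss to a full 20%, so they lean pessimistic.
- **Subgroups are supplementary**, and microscope use may be a fixed feature of the operator or site. The subgroup point is therefore limited to final rinse and file type.

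A reader might go further and infer that unfit teeth are in fact lost after randomisation, because "Endodontic treatment of a tooth with a calcified root canal" and suspected perforation are exclusions (6.3) that preparation can bring to light. The documents do not support that as a fact. Suspicion of perforation is a pre-operative judgement, and eligibility is checked at V0 with a whole-tooth X-ray. Neither condition is among the listed major enrolment breaches (7.6), so such a tooth, if still filled, could remain in mITT and PP. Eligibility breaches are judged blind to the device and to post-randomisation data. Loss follows only for teeth that are never filled or never assessed.

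**Conclusion.** The point holds as an inexpensive design improvement, not as an error in the plan. Allocation is available earlier than needed, unblinded operators can know the arm during preparation, and a randomised patient whose tooth is never filled is analysed nowhere.

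The size is unknown. Under the assumed 2% to 10% loss, power is 1 to 4 points lower than the 79% obtained with no such loss, which is modest. Bias matters more, because the primary analysis is per protocol in a non-inferiority trial. In the constructed case, one to three selectively missing PA1704 failures raise the one-sided error from 5% to between 7% and 15%. That case assumes that only would-be failures leave, and from one arm only. Nothing in the documents indicates that this will happen, or in which direction an imbalance would run.

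**What to change.** Release the eCRF allocation only after the preparation fields are complete and the canal is confirmed ready to fill, immediately before obturation, and at the second session when two are used. Stratification by indication is unaffected, since the indication is known earlier. File type and final rinse then become pre-allocation factors. Count the 80 per arm in allocated patients.

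The patient identifier in 6.6.4 contains the arm letter, so a provisional code without that letter is needed for consent, baseline and any first-session records until allocation.

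Cost: a short amendment, a resequenced eCRF, a small change to the coding scheme, and one chairside eCRF step while the canal is ready. The treatment and the required 66 per group do not change.

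If the sequence can no longer be changed, report all randomised patients by arm, with reasons for any tooth not filled, and add an analysis of all randomised patients with a stated rule for those without an outcome.
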